2. SCHEDULE OF ACTIVITIES (SOA)

Procedure	Screening ¹		Treatment Period ²					Follow-up ¹
	Week -4	Week -2	Day 1	Day 15	Day 29 ³	Day 43	Day 57	Day 70
Informed Consent	X							
Entry Criteria	X ⁴	X ⁴	X ⁴					
Physical, Medical History, Demography, Height	X ^{5,9}	X ^{5,9}	X ^{5,9}					
Weight	X		X	X		X		
HemoCue Hgb	X	X	X	X	X	X	X	
eGFR	X							
Females: Urine Pregnancy Test ⁶	X		X		X		X	X
Females: Estradiol & FSH ⁷		X						
HIV screening and Hepcidin	X							
Randomization			X					
Administration of isotopic iron				X		X		
Blood sampling for isotopic iron					X	X	X	
Crossover ⁸					X			
ECG		X						X
Vital signs	X		X		X		X	X
Clinical chemistry & hematology ¹⁰	X							X
Urinalysis ¹⁰	X							X
Liver chemistry monitoring ¹¹				X		X		
Folate & Vitamin B ₁₂		X						
hsCRP		X						
Ferritin and TSAT		X						
Iron status markers ¹²			X	X	X	X	X	
Indices of erythropoiesis ¹³			X	X	X	X	X	
Blood draw for PGx			X					
AE and SAE Assessment ¹⁴	X ¹⁵	X ¹⁵	X	X	X	X	X	X
Review Concomitant Medications	X	X	X	X	X	X	X	X

- ¹ Allowable time window \pm 3 days.
- ² Allowable time window \pm 2 days.
- ³ All assessments to be performed **PRIOR** to crossing over.
- ⁴ Criteria to be assessed can be found in Section 9.4.1.
- ⁵ Complete physical examination, medical history & demography to be performed at Week -4, while a brief physical examination to be performed at Week -2 and Day 1.
- ⁶ Local urine testing will be standard for the protocol unless serum testing is required by local regulation or IRB/IEC.
- ⁷ As detailed in Inclusion Criteria.
- ⁸ Participants that had been administered daprodustat during treatment Period 1 will be switched to rhEPO, while those on rhEPO will be switched to daprodustat. Examples on switching are provided in the Study Reference Manual (SRM).
- ⁹ Height is only collected at Week -4.
- ¹⁰ Clinical laboratory assessments guidance can be found in Section 9.4.5
- ¹¹ Liver chemistry monitoring guidance can be found in Section 9.4.6.
- ¹² Iron status markers include serum iron, ferritin, transferrin, transferrin saturation (TSAT), soluble transferrin receptor, hepcidin and erythroferrone and are described in Section 9.8.2. All samples for iron status markers to be taken pre dose.
- ¹³ Indices of erythropoiesis include Hgb, hematocrit, red blood cell number, mean corpuscular volume, reticulocyte Hgb and reticulocyte number and are described in Section 9.8.3.
- ¹⁴ Guidance on the timing and need for collection of AEs & SAEs are described in Section 9.2.

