- ¹⁵ SAEs assessed as related to study participation or a GSK product are collected at this visit. See Section 9.2.1 for additional details.

- The timing and number of planned study assessments, including safety or biomarker assessments may be altered during the course of the study based on newly available data to ensure appropriate monitoring.
- Any changes in the timing or addition of time points for any planned study assessments must be documented and approved by the relevant study team member and then archived in the sponsor and site study files but will not constitute a protocol amendment. The IRB/IEC will be informed of any safety issues that require alteration of the safety monitoring scheme or amendment of the ICF.

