Cyst progression in patients with autosomal dominant polycystic kidney disease (ADPKD)	
Published data provide in vivo evidence for a potential role of HIF-1a in the growth of polycystic kidneys; Hif-1a deletion was sufficient to significantly mitigate a progressive polycystic phenotype in an ADPKD mouse model, while conversely pharmacologic HIF-1a stabilization was sufficient to convert a mild polycystic disease into a severely aggravated phenotype with marked loss of renal function. However, the dose of FG-2216 (a PHI) used resulted in a significant erythropoietic response as reflected by ≥10% relative increases in hematocrit over the course of the study. (Kraus, 2018; Hofherr, 2018).
 
A review of the non-clinical data from toxicity studies conducted with daprodustat does not indicate an exacerbation in incidence or severity of kidney cysts in daprodustat-treated animals in comparison to controls. However, the wild type animals used in these toxicity
	
 • Kidney function will be monitored throughout the dosing period as outlined in the SoA (Section 2). • Monitoring of emerging safety data by an internal GSK Safety Review Team.

Potential Risk of Clinical Significance	Summary of Data/Rationale for Risk	Mitigation Strategy
	
studies have a very low background incidence of renal cysts and are not comparable to the mice used in the Kraus article (Kraus, 2018) which are an inducible kidney epithelium-specific Pkd1-deletion model.
 
There is limited experience with daprodustat in subjects with ADPKD in completed clinical trials. In the Japan phase 3 study in non-dialysis subjects, there were 5 subjects with ADPKD (all CKD stage 5) in each treatment group. Mean baseline eGFR was 10 mL/min/1.73m² in the daprodustat subjects vs. 16 mL/min/1.73m² in the rhEPO subjects. The mean (SD) percent change from baseline at Week 52 in eGFR was: -18% (8) vs. -21% (14) in daprodustat vs. rhEPO, respectively.
 
Following review of clinical data received to date, this has not been identified as a safety concern for daprodustat.
	

References

Camposchiaro PA and the first ARVO/Pfizer Institute Working Group *et al.* Ocular versus extraocular neovascularization: Mirror images or vague resemblances. *Invest Ophthalmol & Vis Sci.* 2006; 47:462-474.

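### Appendix 3 says kidney function is monitored throughout dosing per the SoA, but the SoA schedules no kidney test at any of the five treatment-period visits

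*Protocol*

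**What the plan says.** The ADPKD row of Protocol Section 12.3 (Appendix 3) lists two mitigations. The first is "Kidney function will be monitored throughout the dosing period as outlined in the SoA (Section 2". The second is "Monitoring of emerging safety data by an internal GSK Safety Review Team". The same row says "There is limited experience with daprodustat in subjects with ADPKD in completed clinical trials": in the Japanese phase 3 non-dialysis study "there were 5 subjects with ADPKD (all CKD stage 5) in each treatment group". It closes with "Following review of clinical data received to date, this has not been identified as a safety concern for daprodustat".

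The SoA (Protocol Section 2) has three rows that bear on kidney function: eGFR, "Clinical chemistry & hematology", and urinalysis. Table 8 in Appendix 4 places creatinine and BUN in the clinical chemistry panel. A separate liver chemistry row is marked on Days 15 and 43, and Section 9.4.6 limits that panel to ALT, AST, bilirubin and alkaline phosphatase.

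Section 3.3.3 rests its positive benefit:risk conclusion partly on the precautions in Appendix 3. SAP Section 4.4.3.2 lists all laboratory data but summarises none that are collected only at screening and follow-up.

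**The concern.** The mitigation names the SoA as its source, so it can be checked there, and the SoA has no matching entry during dosing. Similar statements in Appendix 3 do hold up. Hemoglobin is measured by HemoCue at all five treatment-period visits, and blood pressure is taken with vital signs on Days 1, 29 and 57.

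What is at stake is a stated safety control, in a population with Stage 3 to 5 CKD. ADPKD is not a listed exclusion, so such participants can enter; the documents give no expected number, and it may be zero. An ethics committee reading Appendix 3 would believe that kidney function is followed on treatment. The sponsor's Safety Review Team would receive no scheduled on-treatment kidney value from this study.

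**Working it through.** The protocol gives no figure to reproduce here. The check sets the Appendix 3 sentence against the SoA, then works out the intervals.

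**Step 1. Kidney-related rows of the SoA, by visit**

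| Assessment | Week -4 | Week -2 | Day 1 | Day 15 | Day 29 | Day 43 | Day 57 | Day 70 |
|---|---|---|---|---|---|---|---|---|
| eGFR | X | | | | | | | |
| Clinical chemistry (creatinine, BUN) | X | | | | | | | X |
| Urinalysis | X | | | | | | | X |
| Liver panel only | | | | X | | X | | |
| Iron markers, erythropoiesis indices | | | X | X | X | X | X | |

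Treatment-period visits with a kidney test: 0 of 5. Blood is drawn at all five.

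**Step 2. Is this a table-reading artefact?** Text outside the table agrees with it. Inclusion criterion 2 confirms CKD stage at Week -4 only. Table 4 (Section 9.4.1) lists eGFR and the safety laboratory tests under Week -4 and not under Week -2 or Day 1. Section 9.4.6 says the liver tests are also done whenever the chemistry panel is done. That adds liver tests at chemistry visits; it does not add creatinine on Days 15 and 43.

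**Step 3. Interval between the two chemistry draws**
- Nominal, from the SoA columns: Week -4 is 28 days before Day 1 and Day 70 is 69 days after it, so 28 + 69 = 97 days.
- With the visit rules combined: Week -4 carries ±3 days, Day 57 carries ±2 days, and Section 5.1 sets follow-up at 14 ± 3 days after the final blood sample. Day 57 is 56 days after Day 1.
  - Shortest: (28 - 3) + (56 - 2) + (14 - 3) = 25 + 54 + 11 = 90 days.
  - Longest: (28 + 3) + (56 + 2) + (14 + 3) = 31 + 58 + 17 = 106 days.

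**Step 4. Where the draws fall relative to daprodustat (nominal days)**
- Sequences C and D (daprodustat in Period 1; 6 of the 12 in Table 1): 28 days before the first dose, and 70 - 28 = 42 days after the last, following 28 days of rhEPO.
- Sequences A and B (daprodustat in Period 2): 28 + 28 = 56 days before the first dose, and 70 - 56 = 14 days after the last.

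**Step 5. What on-treatment tests could show.** The ADPKD row reports mean eGFR changes at Week 52 of -18% (daprodustat, mean baseline 10 mL/min/1.73m²) and -21% (rhEPO, mean baseline 16). Assume even accrual over 364 days, and multiply mean percent change by mean baseline as an approximation:
- 18% × 28/364 = 1.38%; 10 × 0.0138 = 0.14 mL/min/1.73m².
- 21% × 28/364 = 1.62%; 16 × 0.0162 = 0.26 mL/min/1.73m².

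Changes this small over one 28-day period mean that added tests would serve to catch acute changes, not slow progression.

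**The case against.** The strongest reply is that little turns on the sentence. It is one of two mitigations, for a risk that the row itself says has not been identified as a safety concern. Exposure to daprodustat is 28 days per participant. The list of adverse events of special interest (Section 9.2.4) has no renal item, and the only kidney-specific row in Appendix 3 concerns cyst progression, which added tests would not show.

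Other safeguards also exist. Section 7.7.3 expects investigators to monitor clinical status in line with KDIGO or local guidance. Appendix 4 lets them order additional tests. Adverse events are assessed at every treatment-period visit. Exclusion 28 lets an investigator keep out anyone judged to be at unacceptable risk.

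This stands as an argument about importance, and it is why the point is rated low to moderate. It does not make the sentence true: these provisions are general or discretionary, and the sentence describes monitoring that the SoA sets out.

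A reader might infer that the SoA notes already allow a repair without an amendment, since under them a new time point needs only sign-off within the team and the change is "then archived in the sponsor and site study files but will not constitute a protocol amendment". The preceding note ties changes in the timing and number of assessments to newly available data, and none are cited. A file note would also leave the printed SoA, and so the Appendix 3 sentence, uncorrected.

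**Conclusion.** The protocol contradicts itself. A mitigation that Appendix 3 attributes to the SoA is scheduled at none of the five treatment-period visits, and the only scheduled creatinine and BUN values bracket the whole dosing period, nominally 97 days apart (about 90 to 106). Safety importance is low to moderate.

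Three stronger readings are tempting, and the documents support none of them:
- **That the trial's result is compromised.** Kidney function does not enter the primary model, the sample size of 12 or the power calculation.
- **That participants are exposed to a recognised renal hazard.** The row says ADPKD progression has not been identified as a safety concern, although it rests on 5 participants per group and calls experience limited.
- **That scheduled tests would detect cyst progression.** Under even accrual the expected change over 28 days is 1.4% to 1.6%.

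The count of visits and the nominal interval rest on the SoA alone. The wider range assumes that the visit windows and the follow-up rule act independently, and the 28-day figures assume linear decline.

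**What to change.** Amend the protocol by one of two routes.

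**Route 1: deliver the monitoring.** Add serum creatinine, with CKD-EPI eGFR as at Week -4, to the SoA on Days 1, 15 and 43, using blood already drawn. Each participant then has a baseline and one value on each treatment. In the SAP, add eGFR to the laboratory variables in Section 4.4.3.2, and add a renal row to the baseline table in Section 4.1.2 with Day 1 as baseline for both periods, as Section 4.4.3.3 does for vital signs. No Day 29 value is then needed. The existing review-and-repeat rule in Protocol Section 9.4.5 covers the results, so no new stopping rule is proposed.

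Cost: 12 × 3 = 36 results (12 baseline, 12 on daprodustat, 12 on rhEPO), plus 3 for each participant enrolled beyond 12; total enrolment is not stated. There is no extra visit, and no extra draw if the volume already collected suffices (an assumption). Add the amendment and a small SAP edit. The downside is that incidental creatinine changes in Stage 3 to 5 CKD will need review.

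**Route 2: correct the statement.** If the sponsor judges on-treatment testing unnecessary, reword the Appendix 3 mitigation to say that kidney function is checked at Week -4 and at the Day 70 follow-up only. This costs one sentence in an amendment and leaves the study with no scheduled on-treatment kidney data.

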12.4. Appendix 4: Clinical Laboratory Assessments

The tests detailed in [Table 8](#) will be performed by a central laboratory.

- Local laboratory results are only required in the event that the central laboratory results are not available in time for either study treatment administration and/or response evaluation. If a local sample is required, it is important that the sample for central analysis is obtained at the same time. Additionally, if the local laboratory results are used to make either a study treatment decision or response evaluation, the results must be entered into the eCRF.
- Protocol-specific requirements for inclusion or exclusion of participants are detailed in [Section 6](#) of the protocol.
- Additional tests may be performed at any time during the study as determined necessary by the investigator or required by local regulations.

Table 8 Clinical Laboratory Assessments

Assessments	Parameters			
Hematology	Platelet Count RBC Count Hgb Hematocrit	RBC Indices: MCV MCH %Reticulocytes	WBC count with Differential: Neutrophils Lymphocytes Monocytes Eosinophils Basophils	
Clinical Chemistry ¹	BUN	Potassium	Aspartate Aminotransferase (AST)/ Serum Glutamic-Oxaloacetic Transaminase (SGOT)	Total and direct bilirubin
	Creatinine	Sodium	Alanine Aminotransferase (ALT)/ Serum Glutamic-Pyruvic Transaminase (SGPT)	Total Protein
	Glucose	Calcium	Alkaline phosphatase	
Routine Urinalysis	
 • Specific gravity • pH, glucose, protein, blood, ketones, bilirubin, urobilinogen, nitrite, leukocyte esterase by dipstick • Microscopic examination (if blood or protein is abnormal) 			

Assessments	Parameters
Other Laboratory Analyses	
 • Follicle-stimulating hormone and estradiol (as needed in women of non-childbearing potential only) • Urine human chorionic gonadotropin (hCG) pregnancy test (as needed for women of childbearing potential)² • HIV antibody • Folate, high sensitivity C-reactive protein, Vitamin B₁₂ • Serum iron, ferritin, transferrin, transferrin saturation, soluble transferrin receptor, hepcidin, erythroferrone • Hemoglobin, hematocrit, red blood cell number, mean corpuscular volume, reticulocyte hemoglobin, reticulocyte number

¹ Details of liver chemistry stopping criteria and required actions and follow-up assessments after liver stopping or monitoring event are given in Section 8.1.1 and Appendix 2. All events of ALT $\geq 3 \times$ upper limit of normal (ULN) and bilirubin $\geq 2 \times$ ULN (> 35% direct bilirubin) or ALT $\geq 3 \times$ ULN and international normalized ratio (INR) > 1.5, if INR measured, which may indicate severe liver injury (possible Hy’s Law), must be reported as an SAE (excluding studies of hepatic impairment or cirrhosis).

² Local urine testing will be standard for the protocol unless serum testing is required by local regulation or IRB/IEC.

12.5. Appendix 5: Study Governance Considerations

Regulatory and Ethical Considerations

- This study will be conducted in accordance with the protocol and with:
 - Consensus ethical principles derived from international guidelines including the Declaration of Helsinki and Council for International Organizations of Medical Sciences (CIOMS) International Ethical Guidelines
 - Applicable ICH Good Clinical Practice (GCP) Guidelines
 - Applicable laws and regulations
- The protocol, protocol amendments, ICF, Investigator Brochure, and other relevant documents (e.g., advertisements) must be submitted to an IRB/IEC by the investigator and reviewed and approved by the IRB/IEC before the study is initiated.
- Any amendments to the protocol will require IEC/IRB approval before implementation of changes made to the study design, except for changes necessary to eliminate an immediate hazard to study participants.
- The investigator will be responsible for the following:
 - Providing written summaries of the status of the study to the IRB/IEC annually or more frequently in accordance with the requirements, policies, and procedures established by the IRB/EC
 - Notifying the IRB/IEC of SAE or other significant safety findings as required by IRB/IEC procedures
 - Providing oversight of the conduct of the study at the site and adherence to requirements of 21 CFR, ICH guidelines, the IRB/IEC, European regulation 536/2014 for clinical studies (if applicable), and all other applicable local regulations

Financial Disclosure

Investigators and sub-investigators will provide the sponsor with sufficient, accurate financial information as requested to allow the sponsor to submit complete and accurate financial certification or disclosure statements to the appropriate regulatory authorities. Investigators are responsible for providing information on financial interests during the course of the study and for 1 year after completion of the study.

Informed Consent Process

- The investigator or his/her representative will explain the nature of the study to the participant or his/her legally authorized representative and answer all questions regarding the study.
- Participants must be informed that their participation is voluntary. Participants or their legally authorized representative will be required to sign a statement of informed consent that meets the requirements of 21 CFR 50, local regulations,

ICH guidelines, Health Insurance Portability and Accountability Act (HIPAA) requirements, where applicable, and the IRB/IEC or study center.

- The medical record must include a statement that written informed consent was obtained before the participant was enrolled in the study and the date the written consent was obtained. The authorized person obtaining the informed consent must also sign the ICF.
- Participants must be re-consented to the most current version of the ICF(s) during their participation in the study.
- A copy of the ICF(s) must be provided to the participant or the participant's legally authorized representative.
- Participants who are rescreened are required to sign a new ICF.

The ICF may contain a separate section that addresses the use of remaining mandatory samples for optional exploratory research in accordance with SOP-GSKF-410. The investigator or authorized designee will explain to each participant the objectives of the exploratory research. Participants will be told that they are free to refuse to participate and may withdraw their consent at any time and for any reason during the storage period. A separate signature will be required to document a participant's agreement to allow any remaining specimens to be used for exploratory research. Participants who decline to participate will not provide this separate signature.

Data Protection

- Participants will be assigned a unique identifier by the sponsor. Any participant records or datasets that are transferred to the sponsor will contain the identifier only; participant names or any information which would make the participant identifiable will not be transferred.
- The participant must be informed that his/her personal study-related data will be used by the sponsor in accordance with local data protection law. The level of disclosure must also be explained to the participant.
- The participant must be informed that his/her medical records may be examined by Clinical Quality Assurance auditors or other authorized personnel appointed by the sponsor, by appropriate IRB/IEC members, and by inspectors from regulatory authorities.

Publication Policy

- The results of this study may be published or presented at scientific meetings. If this is foreseen, the investigator agrees to submit all manuscripts or abstracts to the sponsor before submission. This allows the sponsor to protect proprietary information and to provide comments.
- The sponsor will comply with the requirements for publication of study results. In accordance with standard editorial and ethical practice, the sponsor will generally support publication of multicenter studies only in their entirety and not as individual site data. In this case, a coordinating investigator will be designated by mutual agreement.

- Authorship will be determined by mutual agreement and in line with International Committee of Medical Journal Editors authorship requirements.

Dissemination of Clinical Study Data

- Where required by applicable regulatory requirements, an investigator signatory will be identified for the approval of the clinical study report. The investigator will be provided reasonable access to statistical tables, figures, and relevant reports and will have the opportunity to review the complete study results at a GSK site or other mutually-agreeable location.
- GSK will also provide the investigator with the full summary of the study results. The investigator is encouraged to share the summary results with the study subjects, as appropriate.
- The procedures and timing for public disclosure of the results summary and for development of a manuscript for publication will be in accordance with GSK Policy.

Data Quality Assurance

- All participant data relating to the study will be recorded on printed or electronic CRF unless transmitted to the sponsor or designee electronically (e.g., laboratory data). The investigator is responsible for verifying that data entries are accurate and correct by physically or electronically signing the CRF.
- The investigator must maintain accurate documentation (source data) that supports the information entered in the eCRF.
- The investigator must permit study-related monitoring, audits, IRB/IEC review, and regulatory agency inspections and provide direct access to source data documents.
- The sponsor or designee is responsible for the data management of this study including quality checking of the data.
- Study monitors will perform ongoing source data verification to confirm that data entered into the eCRF by authorized site personnel are accurate, complete, and verifiable from source documents; that the safety and rights of participants are being protected; and that the study is being conducted in accordance with the currently approved protocol and any other study agreements, ICH GCP, and all applicable regulatory requirements.
- Records and documents, including signed ICF, pertaining to the conduct of this study must be retained by the investigator for 15 years after study completion unless local regulations or institutional policies require a longer retention period. No records may be destroyed during the retention period without the written approval of the sponsor. No records may be transferred to another location or party without written notification to the sponsor.

Source Documents

- Source documents provide evidence for the existence of the participant and substantiate the integrity of the data collected. Source documents are filed at the investigator's site.
- Data reported on the CRF or entered in the eCRF that are transcribed from source documents must be consistent with the source documents or the discrepancies must be explained. The investigator may need to request previous medical records or transfer records, depending on the study. Also, current medical records must be available.
- Definition of what constitutes source data can be found in the SRM.

Study and Site Closure

GSK or its designee reserves the right to close the study site or terminate the study at any time for any reason at the sole discretion of GSK. Study sites will be closed upon study completion. A study site is considered closed when all required documents and study supplies have been collected and a study-site closure visit has been performed.

The investigator may initiate study-site closure at any time, provided there is reasonable cause and sufficient notice is given in advance of the intended termination.

Reasons for the early closure of a study site by the sponsor or investigator may include but are not limited to:

- Failure of the investigator to comply with the protocol, the requirements of the IRB/IEC or local health authorities, the sponsor's procedures, or GCP guidelines
- Inadequate recruitment of participants by the investigator
- Discontinuation of further study treatment development

12.6. Appendix 6: Adverse Events: Definitions and Procedures for Recording, Evaluating, Follow-up, and Reporting

Definition of AE

AE Definition

 An AE is any untoward medical occurrence in a clinical study participant, temporally associated with the use of a study intervention, whether or not considered related to the study intervention. NOTE: An AE can therefore be any unfavorable and unintended sign (including an abnormal laboratory finding), symptom, or disease (new or exacerbated) temporally associated with the use of a study intervention.

Events Meeting the AE Definition

 Any abnormal laboratory test results (hematology, clinical chemistry, or urinalysis) or other safety assessments (e.g., ECG, radiological scans, vital signs measurements), including those that worsen from baseline, considered clinically significant in the medical and scientific judgment of the investigator (ie, not related to progression of underlying disease). Exacerbation of a chronic or intermittent pre-existing condition including either an increase in frequency and/or intensity of the condition. New conditions detected or diagnosed after study intervention administration even though it may have been present before the start of the study. Signs, symptoms, or the clinical sequelae of a suspected drug-drug interaction. Signs, symptoms, or the clinical sequelae of a suspected overdose of either study intervention or a concomitant medication. Overdose per se will not be reported as an AE/SAE unless it is an intentional overdose taken with possible suicidal/self-harming intent. Such overdoses should be reported regardless of sequelae.

Events NOT Meeting the AE Definition

 Any clinically significant abnormal laboratory findings or other abnormal safety assessments which are associated with the underlying disease, unless judged by the investigator to be more severe than expected for the participant's condition. The disease/disorder being studied or expected progression, signs, or symptoms of the disease/disorder being studied, unless more severe than expected for the participant's condition. Medical or surgical procedure (e.g., endoscopy, appendectomy): the condition that leads to the procedure is the AE. Situations in which an untoward medical occurrence did not occur (social and/or convenience admission to a hospital).

- Anticipated day-to-day fluctuations of pre-existing disease(s) or condition(s) present or detected at the start of the study that do not worsen.

Definition of SAE

If an event is not an AE per definition above, then it cannot be an SAE even if serious conditions are met (e.g., hospitalization for signs/symptoms of the disease under study, death due to progression of disease).

A SAE is defined as any untoward medical occurrence that, at any dose:
a. Results in death
b. Is life-threatening The term 'life-threatening' in the definition of 'serious' refers to an event in which the participant was at risk of death at the time of the event. It does not refer to an event, which hypothetically might have caused death, if it were more severe.
c. Requires inpatient hospitalization or prolongation of existing hospitalization In general, hospitalization signifies that the participant has been detained (usually involving at least an overnight stay) at the hospital or emergency ward for observation and/or treatment that would not have been appropriate in the physician’s office or outpatient setting. Complications that occur during hospitalization are AE. If a complication prolongs hospitalization or fulfils any other serious criteria, the event is serious. When in doubt as to whether “hospitalization” occurred or was necessary, the AE should be considered serious. Hospitalization for elective treatment of a pre-existing condition that did not worsen from baseline is not considered an AE.
d. Results in persistent disability/incapacity 
 • The term disability means a substantial disruption of a person’s ability to conduct normal life functions. • This definition is not intended to include experiences of relatively minor medical significance such as uncomplicated headache, nausea, vomiting, diarrhea, influenza, and accidental trauma (e.g., sprained ankle) which may interfere with or prevent everyday life functions but do not constitute a substantial disruption.
e. Is a congenital anomaly/birth defect
f. Other situations: 
 • Medical or scientific judgment should be exercised in deciding whether SAE reporting is appropriate in other situations such as important medical events that may not be immediately life-threatening or result in death or hospitalization but may jeopardize the participant or may require medical or surgical intervention to prevent one of the other outcomes listed in the above definition. These events should usually be considered serious. Examples of such events include invasive or malignant cancers, intensive treatment in an emergency room or at home for allergic bronchospasm, blood dyscrasias or convulsions that do not result in hospitalization, or development of drug dependency or drug abuse.

Definition of Cardiovascular Events

Cardiovascular Events (CV) Definition:

Investigators will be required to fill out the specific CV event page of the CRF for the following AEs and SAEs:
 
 • Myocardial infarction/unstable angina • Congestive heart failure • Arrhythmias • Valvulopathy • Pulmonary hypertension • Cerebrovascular events/stroke and transient ischemic attack • Peripheral arterial thromboembolism • Deep venous thrombosis/pulmonary embolism • Revascularization

Recording AE and SAE

AE and SAE Recording

 • When an AE/SAE occurs, it is the responsibility of the investigator to review all documentation (e.g., hospital progress notes, laboratory, and diagnostics reports) related to the event. • The investigator will then record all relevant AE/SAE information in the eCRF. • It is not acceptable for the investigator to send photocopies of the participant's medical records to GSK in lieu of completion of the GSK/AE/SAE eCRF page. • There may be instances when copies of medical records for certain cases are requested by GSK. In this case, all participant identifiers, with the exception of the participant number, will be redacted on the copies of the medical records before submission to GSK. • The investigator will attempt to establish a diagnosis of the event based on signs, symptoms, and/or other clinical information. Whenever possible, the diagnosis (not the individual signs/symptoms) will be documented as the AE/SAE.
Assessment of Intensity

The investigator will make an assessment of intensity for each AE and SAE reported during the study and assign it to 1 of the following categories:
 
 • Mild: An event that is easily tolerated by the participant, causing minimal discomfort and not interfering with everyday activities. • Moderate: An event that causes sufficient discomfort and interferes with normal everyday activities.

- Severe: An event that prevents normal everyday activities. An AE that is assessed as severe should not be confused with an SAE. Severe is a category utilized for rating the intensity of an event; and both AE and SAE can be assessed as severe.
- An event is defined as ‘serious’ when it meets at least 1 of the predefined outcomes as described in the definition of an SAE, NOT when it is rated as severe.

Assessment of Causality

- The investigator is obligated to assess the relationship between study treatment and each occurrence of each AE/SAE.
- A "reasonable possibility" of a relationship conveys that there are facts, evidence, and/or arguments to suggest a causal relationship, rather than a relationship cannot be ruled out.
- The investigator will use clinical judgment to determine the relationship.
- Alternative causes, such as underlying disease(s), concomitant therapy, and other risk factors, as well as the temporal relationship of the event to study intervention administration will be considered and investigated.
- The investigator will also consult the Investigator’s Brochure (IB) and/or Product Information, for marketed products, in his/her assessment.
- For each AE/SAE, the investigator **must** document in the medical notes that he/she has reviewed the AE/SAE and has provided an assessment of causality.
- There may be situations in which an SAE has occurred, and the investigator has minimal information to include in the initial report to GSK. However, **it is very important that the investigator always make an assessment of causality for every event before the initial transmission of the SAE data to GSK.**
- The investigator may change his/her opinion of causality in light of follow-up information and send an SAE follow-up report with the updated causality assessment.
- The causality assessment is one of the criteria used when determining regulatory reporting requirements.

Follow-up of AE and SAE

- The investigator is obligated to perform or arrange for the conduct of supplemental measurements and/or evaluations as medically indicated or as requested by GSK to elucidate the nature and/or causality of the AE or SAE as fully as possible. This may include additional laboratory tests or investigations, histopathological examinations, or consultation with other health care professionals.
- If a participant dies during participation in the study or during a recognized follow-up period, the investigator will provide GSK with a copy of any post-mortem findings including histopathology.
- New or updated information will be recorded in the originally completed eCRF.
- The investigator will submit any updated SAE data to GSK within 24 hours of receipt of the information.

Reporting of SAE to GSK

SAE Reporting to GSK via Electronic Data Collection Tool

- The primary mechanism for reporting SAE to GSK will be the electronic data collection tool.
- If the electronic system is unavailable, then the site will use the paper SAE data collection tool (see next section) in order to report the event within 24 hours.
- The site will enter the SAE data into the electronic system as soon as it becomes available.
- The investigator or medically-qualified sub-investigator must show evidence within the eCRF (e.g., check review box, signature, etc.) of review and verification of the relationship of each SAE to IP/study participation (causality) within 72 hours of SAE entry into the eCRF.
- After the study is completed at a given site, the electronic data collection tool will be taken off-line to prevent the entry of new data or changes to existing data.
- If a site receives a report of a new SAE from a study participant or receives updated data on a previously reported SAE after the electronic data collection tool has been taken off-line, then the site can report this information on a paper SAE form (see next section) or to the Medical Monitor by telephone.
- Contacts for SAE reporting can be found in the SRM.

SAE Reporting to GSK via Paper CRF

- Facsimile transmission of the SAE paper CRF is the preferred method to transmit this information to the Medical Monitor.
- In rare circumstances and in the absence of facsimile equipment, notification by telephone is acceptable with a copy of the SAE data collection tool sent by overnight mail or courier service.
- Initial notification via telephone does not replace the need for the investigator to complete and sign the SAE CRF pages within the designated reporting time frames.
- Contacts for SAE reporting can be found in SRM.

